### Figure 4-1. Treatment Scheme

\*: Biopsy    tt: Target Trough level  
LD: 0.1 mg/kg/day    SOC: Standard of Care

## 5 Population

Male and female renal transplantation patients, 18 to 65 years of age, receiving a cadaveric, or non-HLA identical living related donor kidney may enter the study. It is anticipated that MGTI will enroll approximately 50 patients. Patients who discontinue the study prematurely will not be replaced.

### 5.1 Inclusion Criteria

Patients eligible for inclusion in this study have to fulfill all of the following criteria:

- Male or female recipients 18-65 years of age undergoing primary or secondary kidney transplantation
- Recipients of primary or secondary cadaveric, DCD and elevated KDPI kidney (defined as follows)
  - Donor whose heart has irreversibly stopped beating, previously referred to as non-heart-beating or asystolic donation

**OR**

- Donor with a KDPI  $\geq 70$

- Patients who have given written informed consent to participate in the study

## 5.2 Exclusion Criteria

- Cold ischemic time (CIT) > 30 hours
- Patients who are ABO incompatible, or T, or B cell crossmatch positive
- Patients with a known hypersensitivity to any of the study drugs or to drugs of similar chemical class
- Donor age >70
- Patients with BMI >35 at baseline before surgery
- Pregnant or lactating females
- Females of childbearing potential unwilling to use an effective means of contraception or are planning to become pregnant
- Patients with platelet count <100,000/mm^3 at the evaluation before randomization.
- Patients with an absolute neutrophil count of < 1,500/mm^3 at baseline before surgery or white blood cell count of < 4,500/mm^3
- Patients who are recipients of multiple solid organ transplants
- Patients who have severe hypercholesterolemia (>350 mg/dL) or hypertriglyceridemia (>500 mg/dL). Patients with controlled hyperlipidemia are acceptable
- Patients who have an abnormal liver profile such as ALT, AST, Alk Phos or total bilirubin >3 times the upper normal limit
- Patients who are treated with drugs that are strong inducers or inhibitors of cytochrome P450 3A4, such as terfenadine, astemizole, cisapride, erythromycin, azithromycin, itraconazole, rifampin or lovastatin
- Patients who received an investigational drug or who have been treated with a non-protocol immunosuppressive drug or treatment within 30 days or 5 half-lives prior to randomization
- Patients with a history of malignancy of any organ system, treated or untreated, within the past 2 years whether or not there is evidence of local recurrence or metastases, with the exception of localized basal cell carcinoma of the skin
- Patients who are HIV positive or Hepatitis C (PCR+ only) or Hepatitis B surface antigen positive
- Recipients of organs from donors who test positive for Hepatitis B surface antigen or Hepatitis C (PCR+ only)
- Patients with a history of severe diarrhea, active peptic ulcer disease, or uncontrolled diabetes mellitus (Hgb A1c <7.0 %) at baseline
- Patients who have any surgical or medical condition, which in the opinion of the investigator, might significantly alter the absorption, distribution, metabolism and excretion of study medication, and/or the presence of severe diarrhea or active peptic ulcer
- Patients who have cardiac failure (e.g. resting dyspnea, symptoms with less than ordinary activity, marked limitation of activity) at time of screening or any other severe cardiac disease as determined by the investigator

- Patients with abnormal physical or laboratory findings of clinical significance within 3 months of randomization which would interfere with the objectives of the study
- Patients with any history of coagulopathy or medical condition requiring long-term anticoagulation therapy after transplantation (Low dose aspirin treatment is allowed)
- Patients with known history of focal segmental glomerulosclerosis
- Presence of psychiatric illness (i.e., schizophrenia, bipolar, major depression) that, in the opinion of the investigator, would interfere with study requirements

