## Exclusion criteria

- Cold ischemic time (CIT) > 30 hours
- ABO incompatible transplants, or T, or B cell crossmatch positive transplant
- Patients with a known hypersensitivity to any of the study drugs or to drugs of similar chemical classes
- Non-controlled DCD
- Donor age >70
- Patients with BMI >35 at baseline before surgery
- Pregnant or lactating females
- Females of childbearing potential unwilling to use an effective means of contraception or are planning to become pregnant
- Patients with platelet count <100,000/mm^3 at the evaluation before randomization.
- Patients with an absolute neutrophil count of < 1,500/mm^3 at baseline before surgery or white blood cell count of < 4,500/mm^3
- Patients who are recipients of multiple solid organ transplants
- Patients who have severe hypercholesterolemia (>350 mg/dL) or hypertriglyceridemia (>500 mg/dL). Patients with controlled hyperlipidemia are acceptable
- Patients who have an abnormal liver profile such as ALT, AST, Alk Phos or total bilirubin >3 times the upper normal limit
- Patients who are treated with drugs that are strong inducers or inhibitors of cytochrome P450 3A4, such as terfenadine, astemizole, cisapride, erythromycin, azithromycin, itraconazole, rifampin or lovastatin
- Patients who received an investigational drug or who have been treated with a non-protocol immunosuppressive drug or treatment within 30 days or 5 half-lives prior to randomization
- Patients with a history of malignancy of any organ system, treated or untreated, within the past 2 years whether or not there is evidence of local recurrence or metastases, with the exception of localized basal cell carcinoma of the skin
- Patients who are HIV positive or Hepatitis C (PCR+ only) or Hepatitis B surface antigen positive
- Recipients of organs from donors who test positive for Hepatitis B surface antigen or Hepatitis C (PCR+ only)
- Patients with a history of severe diarrhea, active peptic ulcer disease, or uncontrolled diabetes mellitus (Hgb A1c <7.0 %) at baseline
- Patients who have any surgical or medical condition, which in the opinion of the investigator, might significantly alter the absorption, distribution, metabolism and excretion of study medication, and/or the presence of severe diarrhea or active peptic ulcer

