### **3.2 Secondary objectives**

The key secondary objective is to compare renal function of the everolimus treatment arms to the MMF/MPA treatment arm at 12 and 24 months post-transplantation. Renal function will be measured by the calculated glomerular filtration rate (GFR), using the MDRD (Modification of Diet in Renal Disease) formula (20).

Other secondary objectives include:

- The incidence of treated BPAR at 12 months
- The incidence of graft loss at 12 months
- The incidence of death or loss to follow up at 12 months
- Incidence of adverse events (AEs)
- Incidence of serious adverse events (SAEs)
- Incidence of new onset diabetes mellitus defined as non-diabetic patients before transplantation, who are receiving glucose lowering treatment for more than 30 days

post-transplant, or with a random plasma glucose  $\geq 200$  mg/dL (11.1 mmol/L) with 2 fasting plasma glucose values  $\geq 126$  mg/dL (7 mmol/L).

- Incidence of CMV (viremia or viruria) and BKV (viremia or viruria)
- Incidence of proteinuria by more than 3 fold or proteinuria reaching 1.5gm/day
- The comparison of the health related quality of life for patients treated with everolimus plus low dose tacrolimus to CellCept plus standard dose tacrolimus

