## **7.2 Patient demographics/other baseline characteristics**

After informed consent has been signed and the patient's eligibility to participate in the study has been determined, baseline patient information will be obtained, such as date of birth, age, sex, race, full relevant medical history/current medical conditions, information on renal transplantation background of recipient and donor and on transplantation procedure.

Baseline assessments will occur in the time period starting 30 days pre-transplantation and ending at the time of transplant. Results of a physical examination at a baseline, include pregnancy test (within 48 hours prior to transplantation), vital signs, blood chemistry and hematology, urinalysis, including a quantitative protein/creatinine ratio.

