### **7.5.8 Clinical chemistry**

Sodium, potassium, chloride, calcium, magnesium, inorganic phosphate, blood urea nitrogen, creatinine, glucose, uric acid, AST, ALT, alkaline phosphatase, total bilirubin, total cholesterol, HDL, LDL, triglycerides, CPK, lipase, and amylase will be assessed at hospital affiliated laboratory. The blood chemistry will be measured at Baseline, on Day 1, 3, and 5; Weeks 1, 2, and 4; Months 2, 3, 4, 6, 8, 10, 12, 15, 18, 21, and 24. LDL and HDL will be measured only at Baseline, Week 4, Months 6 and 12.

Random or fasting plasma glucose values as needed to rule out or confirm suspected new onset of diabetes.

If the CPK level is above the upper limit of normal, CK-MB fraction will be measured.

If the total bilirubin concentration is greater than 1.5 times the upper limit of normal, total bilirubin should be differentiated into the direct and indirect reacting bilirubin.

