### **10.1 Populations for analysis**

Full Analysis Set (FAS; intent-to-treat) consists of all randomized patients who received at least one dose of study drug. Following the intent-to-treat principle, patients will be analyzed according to the treatment they were assigned to at randomization.

Safety Set (SS) consists of all patients who received at least one dose of study drug and had at least one post-baseline safety assessment. Patients will be analyzed according to treatment received. Of note, the statement that a patient had no adverse events also constitutes a safety assessment.

Per Protocol Set (PPS) consists of all FAS patients without a major protocol violation and/or deviation, and who have completed the study. Analysis will be conducted in this set as well.

Efficacy analysis will be performed on the FAS, as defined above, with patient data analyzed according to the treatment groups to which they were randomized. It will also be done on the SS and PPS with patient assignment as treatment actually received.

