### **10.5.2 Safety**

Safety variables to be assessed include discontinuation from study, discontinuation from treatment, renal function, AE/infection, SAE, notable events, laboratory tests, and vital signs.

Comparison of calculated GFR using an analysis of covariance (ANCOVA) with baseline (Month 1) GFR as a covariate, and treatment and induction therapy as main effects, will be performed. Month 24 GFRs will be divided into three categories (<30, 30-60, >60) to classify chronic kidney disease. The proportion of patients in certain categories will be compared between treatment groups using the Cochran-Mantel-Haenszel test controlling for the Month 1 category.

Other safety variables include incidences of AEs, SAEs, new onset diabetes mellitus, CMV, BKV and proteinuria. These incidences will be compared between treatment groups using a Cochran-Mantel-Haenszel test, stratified by induction therapy. Urine protein/creatinine ratios will be compared between treatment groups using the Wilcoxon Rank-Sum test.

Additional assessments of safety will be based on the frequency of adverse events and on the number of laboratory values that fall outside of pre-determined notable ranges. Other safety data (e.g. vital signs and special tests) will be considered as appropriate. The data collected will be presented in listings, summary tables and graphs. All analyses will be performed on the SS.

Adverse events will be summarized by presenting, for each treatment group, the number and percentage of patients having any adverse event, having an adverse event in each body system and having each individual adverse event. The same type of summaries will be provided for serious adverse events and for events suspected to be related to the study medication. Any other information collected (e.g. severity or relatedness to study medication) will be listed as appropriate.

Laboratory data will be summarized by presenting shift tables using notable ranges (baseline to most extreme post-baseline value), by presenting summary statistics of raw data and change from baseline values (means, medians, standard deviations, ranges) and by the flagging of notable values in data listings.

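### The diabetes exclusion contradicts itself (uncontrolled, but HbA1c below 7.0%) in both places it appears; as a lesser item, Table 13-1 flags low rather than high urine protein/creatinine

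*Combined protocol and SAP*

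**What the plan says.** **Diabetes exclusion.** Section 5.2 excludes patients with "uncontrolled diabetes mellitus (Hgb A1c <7.0 %) at baseline". The synopsis has the same criterion with the same sign: "Patients with a history of severe diarrhea, active peptic ulcer disease, or uncontrolled diabetes mellitus (Hgb A1c <7.0 %) at baseline". No other HbA1c limit appears in the document.

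**Neighbouring text.** In the same list, the lipid criterion puts a greater-than sign on the severe state (cholesterol above 350 mg/dL, triglycerides above 500 mg/dL) and adds that "Patients with controlled hyperlipidemia are acceptable". Section 3.2 defines new-onset diabetes by glucose-lowering treatment or by high glucose.

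**Scheduled measurements.** The baseline assessments in section 7.2 include "vital signs, blood chemistry and hematology, urinalysis, including a quantitative protein/creatinine ratio". The chemistry panel in section 7.5.8 includes "blood urea nitrogen, creatinine, glucose, uric acid, AST, ALT" and further analytes. Neither names HbA1c.

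**Use in the analysis.** Under section 10.1 the Per Protocol Set "consists of all FAS patients without a major protocol violation and/or deviation, and who have completed the study", and efficacy is analysed in that set as well as in the Full Analysis Set.

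**Protein/creatinine.** Table 13-1 in Appendix 1, headed as criteria for notable abnormalities, lists urine protein/creatinine at <200 mg/g and <22.7 mg/mmol. Section 3.2 has as a secondary objective "Incidence of proteinuria by more than 3 fold or proteinuria reaching 1.5gm/day". Section 10.5.2 uses the notable ranges for counts of laboratory values, shift tables and flags in listings.

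**The concern.** An eligibility criterion has to give the same answer whoever applies it. Here the word and the number point in opposite directions, so the answer depends on which one the screener trusts. Two things are at stake. The first is who is enrolled: read literally, the number admits the patients the criterion is meant to keep out. The second is who can later be called an eligibility violation. A monitor who applies the printed number and an investigator who applies the word would disagree about the same diabetic patient. That disagreement can carry through to the Per Protocol Set and to the reporting of major deviations to the IRB under section 12.

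The Table 13-1 row looks like the same kind of slip. As printed, the notable-value output would mark patients with little protein in the urine and miss those with a lot.

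**Working it through.** **1. The exclusion under each reading.** The text gives one threshold, 7.0%. To compare the readings, I assume that 7.0% stays the cut-point when the word is followed. This is for illustration and does not propose a limit. For a patient with diabetes:

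| HbA1c | Following the number | Following the word |
|---|---|---|
| 6.0% | excluded | admitted |
| 6.9% | excluded | admitted |
| 7.0% | admitted | excluded |
| 8.5% | admitted | excluded |

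Every value changes side. A third reading, in which a patient must be both uncontrolled and below 7.0%, would exclude almost nobody.

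**2. Which reading the plan's own usage supports.** The lipid criterion marks the severe state with a greater-than sign and accepts controlled patients. Section 3.2 places diabetes at high glucose. Both agree with the word and not with the sign.

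**3. Could the sign be a text-extraction fault?** The same sign is printed in two separate lists, and neighbouring limits read sensibly in both directions (BMI >35, liver tests >3 times the upper limit, platelets <100,000/mm³). A fault is unlikely but cannot be fully excluded from the text alone.

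**4. Number of patients.** Inputs: 48 patients and 16 per arm (section 10.6), and the pilot basis of 12 per group (same section). Diabetes prevalence is not given, so 10% to 40% is assumed. Under the cut-point in step 1, each diabetic patient is eligible under exactly one of the two readings, so the ceiling is the number of diabetic patients:

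- 0.10 × 48 = 4.8, about 5
- 0.40 × 48 = 19.2, about 19

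Weight of one patient removed from the Per Protocol Set:

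- 1/16 = 6.25% of a full arm
- 1/12 = 8.3% of the 12 per arm

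**5. Protein/creatinine row.** Unit check, with creatinine at 0.11312 g/mmol: 200 mg/g × 0.11312 = 22.6 mg/mmol, against 22.7 printed, a difference of 0.3%. The two columns state the same cut-off in the same direction, so both need attention.

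As printed, 50 and 199 mg/g are flagged, while 200, 1,500 and 3,000 mg/g are not. The 1.5 g/day level in section 3.2, converted with assumed creatinine excretion of 2.0, 1.5, 1.0 and 0.8 g/day, is:

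- 1,500/2.0 = 750 mg/g
- 1,500/1.5 = 1,000 mg/g
- 1,500/1.0 = 1,500 mg/g
- 1,500/0.8 = 1,875 mg/g

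All are above 200 mg/g and would not be flagged.

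**The case against.** The strongest reply is that a transplant clinician will see a slipped sign and read past it. The plan's own usage points that way, and nothing shows the number being applied. That may describe what happens at the bedside, but it does not give an auditable criterion. The exclusion for clinically significant laboratory findings in the same list leaves discretion without saying which reading applies.

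Several narrower points stand:

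- The exact reversal holds only if 7.0% remains the cut-point, since the word alone carries no threshold. It is the only threshold the text gives.
- The range of 5 to 19 is a ceiling under an assumed prevalence, not an estimate.
- The plan does not define a major violation, so removal from the Per Protocol Set is possible rather than certain. Section 10.4.2 bases the primary analysis on the Full Analysis Set.
- Table 7-1 has a single row for laboratory tests, so the absence of HbA1c there proves nothing. The omission from sections 7.2 and 7.5.8 is the real evidence.

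On the protein/creatinine row, section 10.5.2 speaks of values outside the notable ranges, so the entry might be taken as a normal range. The table heading and the other rows with limits tell against this, because they list abnormal values.

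**Conclusion.** The concern holds. The diabetes exclusion is wrong as written in both places, and it should be corrected because it decides who enters the trial. The contradiction itself rests on no assumption; only the patient count does.

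The damage has clear limits. Eligibility comes before the 1:1:1 randomization, so the between-arm comparison in the Full Analysis Set is not biased. New-onset diabetes is counted only in patients who were not diabetic before transplantation, so that endpoint is unaffected. What remains is the make-up of the enrolled sample and, potentially, membership of the Per Protocol Set.

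The protein/creatinine row is also in the wrong direction, with smaller consequences: three descriptive outputs (notable-value counts, shift tables and listing flags). The proteinuria incidence endpoint, its Cochran-Mantel-Haenszel test and the Wilcoxon comparison of ratios do not use this cut-off.

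**What to change.** - Reconcile the word and the inequality in the synopsis and in section 5.2, so that the criterion excludes the group it names. The sponsor should confirm the threshold; none is proposed here.
- Add one line saying where the HbA1c value comes from and how recent it must be.
- If enrolment has begun, check the screening log and the enrolled diabetic patients against the reconciled text. State whether a mismatch counts as a major violation for the Per Protocol Set.
- Reconcile the protein/creatinine row of Table 13-1 with section 3.2 in both unit columns, so that high values are flagged. The sponsor should confirm the cut-off.

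The cost is four text entries and one added line in a short amendment, plus the log check if patients have already been screened.

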## 6 Treatment

The study is open label. Patients will receive either everolimus or MMF/MPA.

### 6.1 Investigational and Control Drugs

- Investigational drug: Everolimus (ERL) will be provided as 0.75 mg tablets (10 tablets/blister). Additionally, 0.5 mg tablets (10 tablets/blister) will be supplied for dose adjustments based on blood levels, tolerability, change in co-medications or clinical conditions. Everolimus tablets are white to yellowish, marbled, round, flat with beveled edge.
- Control drug: Mycophenolate Mofetil (MMF)

Investigational or control drug will be administered in combination with tacrolimus (TAC).

### 6.2 Treatment Arms

Within 24 hours after transplantation, after having met all inclusion/exclusion criteria, patients will be randomized to one of the following treatment groups in a ratio of 1:1:1. All patients will receive Campath or Simulect as induction therapy as well as Solumedrol infusion.

#### Investigational Drug

**Arm 1:** Concentration controlled ERL + Low dose TAC + Corticosteroid withdraw

**Arm 2:** Concentration controlled ERL + Low dose TAC -> MMF/MPA at Month 3 + Corticosteroid withdraw

#### Control Drug

**Arm 3:** Standard dose TAC + MMF/MPA + Corticosteroid withdraw

### 6.3 Treatment Assignment

Once a potential study patient is identified and he/she fulfills the inclusion/exclusion criteria and the informed consent form is signed, the patient will be entered into the study.

The patient will be assigned a patient identification number sequentially ( 001, 002 etc) Randomization will be performed by the Principal Investigator and/or the clinical research

coordinator using randomization envelopes which each have been randomly assigned a treatment group. A total of 16 patients will be randomized into each treatment group.

If a patient fulfills the conditions to be randomized, the study team will notify Research Pharmacy staff with the treatment arm and a subject ID number. The Research Pharmacy will then dispense the assigned drug accordingly.

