#### **4 Study Design**

This is a 24 month, Single Center, Open-Label, Randomized, Parallel assignment, non-inferiority pilot study of safety and efficacy, comparing Everolimus with low-dose Tacrolimus (2 arms; 1 arm will involve a conversion to MMF/MPA at month 3) and the standard of care (with standard dose Tacrolimus and MMF/MPA) in recipients of DCD and elevated KDPI kidneys. For this study, either MMF 1,000 mg BID or MPA 720 mg BID will be allowed since MMF and MPA are considered to be therapeutically equivalent.

All study patients must give a signed informed consent voluntarily prior to any study-related activities. Once a signed consent is obtained, baseline assessment including laboratory testing will take place to determine patient's eligibility to participate in the study. Baseline assessments will occur in the time period starting 3 weeks pre-transplantation and ending at the time of transplantation. Eligible patients will receive Campath or Simulect as an induction therapy according to the institutional practice.

Randomization will occur within 24-hour of transplantation. Fifty patients who meet the inclusion/exclusion criteria will be randomized to receive their first dose of study drug (0.75 mg Everolimus (2 arms) or 1,000/720 mg MMF/MPA) within 24 hours of transplantation (Figure 4-1). The first dose of Tacrolimus will be given to all study participants according to our standard practice. Patients will be assigned to either continuation on low-dose Tacrolimus (Arm 1), to conversion from low-dose Tacrolimus to Mycophenolate at month 3 (Arm 2), or to standard therapy with Tacrolimus and Mycophenolate (Arm 3).

Everolimus and Tacrolimus levels will be monitored throughout the study, and respective doses will be adjusted according to the desired trough levels. Patients will be started on 0.75mg BID. Everolimus will be dosed to target trough levels of 3 to 8 ng/ml, starting on Day 7.

Earlier increase in Everolimus level may decrease Tacrolimus exposure, which may lead to under-immunosuppression; increasing the risk of acute rejection (16). Therefore, Day 7 $\pm$ 1 was chosen to initiate the first dose adjustment for Everolimus after careful consideration of the half-life of this drug and turnaround time of the trough level availability. The target Everolimus trough level was determined based on the Novartis B201 and B251 studies (17).

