## **6.4 Treatment Blinding**

This is an open-label study. Therefore, after randomization, the investigator, pharmacist and patient will be aware of which treatment is administered to the patient. The investigator should, however, withhold the treatment assignment from the local pathologist interpreting the biopsies. The local pathologist will provide the investigator their interpretation for clinical management of the patient.

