#### **10.6 Sample size calculation**

Since this is a pilot study, the sample size estimation method proposed by Julious was considered in order to minimize the sample size (14). Julious proposes to employ sample size of 12 per group for a pilot study (14). Assuming the drop out rate of 20% along with the ease of blocked randomization, we propose the sample size of 16 per arm, totaling 48 patients. The estimated effect size,  $\alpha$ , and  $\beta$  corresponding to this sample size are 0.9, 0.05 (two-sided), and 0.2 respectively (15). A block size of 12 along with an allocation ratio of 1:1:1 will be employed as a randomization scheme.

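### The team that judges eligibility also opens the envelopes in an open-label, single-centre trial with one printed block size of 12, so about one assignment in nine can be known in advance

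*Combined protocol and SAP*

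**What the plan says.** **Who allocates, and how.** Section 6.3 (Treatment Assignment): "Randomization will be performed by the Principal Investigator and/or the clinical research", and the sentence continues "coordinator using randomization envelopes which each have been randomly assigned a treatment group". The section then says that "the study team will notify Research Pharmacy staff with the treatment arm and a subject ID number", so the arm passes from the team to the pharmacy. It does not say that the envelopes are sealed, opaque, numbered in sequence or held by someone independent.

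**Who knows past assignments.** Section 4 (Study Design): "This is a 24 month, Single Center, Open-Label, Randomized, Parallel assignment, non-inferiority pilot study". Section 6.4 (Treatment Blinding): "after randomization, the investigator, pharmacist and patient will be aware of which treatment is administered to the patient".

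**The scheme.** Section 10.6 (Sample size calculation): "A block size of 12 along with an allocation ratio of 1:1:1 will be employed as a randomization scheme", and "we propose the sample size of 16 per arm, totaling 48 patients". The synopsis repeats both. No variation in block size and no strata are described.

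**Related text that does not agree.** Section 6.5.2 has the pharmacy select drug by randomization numbers on the pack labels, tied to a confidential list. Section 10.4.2 refers to stratification factors applied at randomization. Sections 10.4.4, 10.5.1 and 10.5.2 stratify or adjust analyses by induction therapy.

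**The concern.** Someone who knows the block size and every past assignment can count what is left in the current block. Sealing the envelopes or keeping the list confidential does not prevent this, because the inference needs neither.

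Here the block size is printed in the protocol, all assignments are made by one team, and that team also decides eligibility. Several exclusions in Section 5.2 rest on judgement: conditions that might alter drug handling, severe cardiac disease, abnormal findings that would interfere with the objectives, and psychiatric illness. A patient could be ruled out under one of these by someone who knows, or has a good idea of, which arm comes next. Section 4 itself anticipates wound-healing complications on everolimus, so a recruiter could have a reason to hesitate over a particular patient.

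What is at stake is the comparability of the arms. With 16 patients per arm, one patient moves an arm's failure rate by 1/16 = 6.25 percentage points. Analysis by randomized arm (Section 10.1) does not help, because the selection happens before randomization. Blinding the pathologist (Section 6.4) protects the biopsy reading but not the choice of who enters.

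**Working it through.** **Inputs.** Block of 12 at 1:1:1, hence 4 per arm per block (Section 10.6); 48 patients (Section 10.6); all earlier assignments known (Sections 4 and 6.4). Assumption: one unstratified list, used in order.

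**The plan's own figure.** 12 per arm with 20% dropout gives 12/0.8 = 15. Raising 15 to 16 gives 3 × 16 = 48 = 4 complete blocks of 12. The sample size therefore fits the stated block size.

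**Assignments certain in advance.** With *r* places left in a block, the next assignment is certain only if all *r* belong to the same arm. The probability is 3·C(4,*r*)/C(12,*r*).

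| Position in block | *r* | Probability certain |
|---|---|---|
| 12 | 1 | 1 |
| 11 | 2 | 18/66 = 0.273 |
| 10 | 3 | 12/220 = 0.055 |
| 9 | 4 | 3/495 = 0.006 |
| 1 to 8 | 5 to 12 | 0 |

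The sum is 1.33 per block. Over four blocks this is 5.3 of 48, or 11.1%. At least 4 are guaranteed, the last of each block.

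**Everolimus or control known in advance.** This needs the remaining places to hold no control assignment or only control assignments: [C(8,*r*) + C(4,*r*)]/C(12,*r*). For *r* = 1 to 8 this gives 1, 0.515, 0.273, 0.143, 0.071, 0.030, 0.010 and 0.002. The sum is 2.04 per block, or 8.2 of 48 (17.0%).

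**At least one arm ruled out.** Exact enumeration gives 3.47 per block, or 13.9 of 48 (28.9%). This always holds for positions 11 and 12.

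**Best guess.** Naming the arm with most places left succeeds, for positions 1 to 12, with probability 0.333, 0.364, 0.400, 0.412, 0.427, 0.459, 0.476, 0.497, 0.552, 0.588, 0.636 and 1. The sum is 6.144, and 6.144/12 = 51.2%, or 24.6 of 48. Unpredictable allocation would give 33.3%, or 16 of 48.

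**Alternative block schemes.** A smaller fixed block is worse: 20% of assignments are certain with a block of 6 and 33% with a block of 3. For varying blocks, a simulation of 4,000 runs assumed that the recruiter knows the set of sizes but not their order. The sets themselves are assumptions.

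| Scheme | Certain, of 48 | Best guess right |
|---|---|---|
| Fixed 12 (exact) | 5.3 | 51% |
| Varying 6, 9, 12 | 1.2 | 52% |
| Varying 3, 6, 9 | 1.7 | 55% |

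Varying the block size removes most of the certainty but does not reduce guessing.

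**The case against.** **Most assignments cannot be deduced.** This stands. About 89% are not certain, none of the first eight in a block ever is, and the best guess is wrong about half the time. Among fixed blocks, 12 is less predictable than 6 or 3. A reader might infer that the next arm is usually known, but the figures do not support that.

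**Steering a patient toward a chosen arm is hard.** This largely stands. It would mean waiting for someone else to use the current envelope, and Section 6.2 sets randomization within 24 hours of transplantation. With 48 to 50 patients over 24 months (about 730 days), enrolments come roughly every 15 days. If arrivals are evenly random, the chance of another within 24 hours is about 1 − exp(−1/15) = 6% to 7%. Keeping a patient out is the more realistic route.

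**Exclusion leaves a trail.** This stands in part. Section 6.5.1 assigns a number at consent, never reuses it, and logs the reason for non-randomization. It does not cover patients who are never approached, and a reason based on judgement is hard to challenge afterwards. The limits on CIT, donor age and KDPI are numeric, so the judgement criteria give no specific route for excluding a poor donor kidney.

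**A confidential list exists.** Section 6.5.2 says so, but past assignments and the printed block size are enough for the deduction.

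**Randomization may be stratified.** Section 10.4.2 implies it, so absence of stratification cannot be stated as fact. No strata are defined in Section 6.3 or 10.6. Blocks within strata would remain deducible to someone tracking each stratum, although incomplete blocks would lower the count slightly.

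**Conclusion.** The concern holds as a modest but real weakness in allocation concealment. On one unstratified list of 48, about 5 assignments (11%) are certain in advance, the everolimus-or-control contrast is known for about 8 (17%), and a best guess succeeds 51% of the time against 33%. Section 4 gives 50 randomized patients rather than 48. The two extra would fall at the start of a fifth block and add no certain assignments.

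These figures measure predictability, not bias. A reader might infer that enrolment was steered or that the primary comparison is biased by a known amount. The documents report no steering, and nothing in them allows the bias to be sized. What they show is an avoidable opportunity for selective exclusion before randomization, which the planned analyses cannot correct. Pilot status lowers the consequences but does not remove the reason to close the gap.

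**What to change.** 1. Have the contracted statistician (Section 10) generate the list with randomly varying block sizes, held in a document the recruiters do not see. Remove the block size from Section 10.6 and the synopsis.
2. Have the Research Pharmacy, or a central system if one is available, hold the list and release the arm only after eligibility and entry are irrevocably recorded. This is the main protection, because varying the blocks cuts certain assignments but not guessing. Section 9.1 describes REDCap only as a database, so a randomization function there would have to be confirmed.
3. Reconcile Section 6.3, where the team tells the pharmacy the arm, with Section 6.5.2, where labels are tied to a confidential list.
4. Reconcile Section 10.4.2 with Section 10.6: define the strata used at randomization, or delete the reference to them.

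The cost is a short amendment and set-up time at the pharmacy. The main burden is that release must be available throughout the 24-hour window after transplantation, including nights and weekends. The documents do not show whether present pharmacy cover allows this.
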